Specific Aim 3: Conduct a pilot randomized controlled trial of the brief, Veteran-targeted PCI in a sample of recent Veterans with stress-related mental health disorders (n=48) to assess feasibility and preliminary efficacy.

Hypothesis 3a: The brief PCI will be shown to be feasible as evidenced by successful rates of recruitment, attendance at intervention sessions by Veterans, and interventionist fidelity to the intervention.

Hypothesis 3b: Compared to a health and wellness control intervention, participation in the brief, Veteran targeted PCI will result in significant increases in (1) Veteran PCC behaviors in mental health care encounters and (2) functioning in domains of health, purpose, and community.

Secondary analysis: Comparing the RCT arms, explore (1) Veteran attrition from VA mental health care via chart review and (2) Veteran self-assessment of levels of clinical symptomology with the DASS-21, AUDIT, DAST 10, and PCL-5.

2 * Discuss the research design including but not limited to such issues as: probability of group assignment, potential for subject to be randomized to placebo group, use of control subjects, etc.:

Aim 1: 35 recent Veterans with stress-related mental health disorders and their VA mental health providers will consent to audio-recording of one treatment encounter. (There is no randomization or group assignment.)

Aim 2: Two focus groups of 4-6 Veterans each will be held. We will also conduct a clinical demonstration of the PCI with 10 Veterans to examine acceptability and further refine the intervention. Participants will complete the three session intervention and participate in a qualitative interview about their experience. (There is no randomization or group assignment.)

Aim 3: We will conduct a pilot randomized controlled trial of the PCI (n=48) to assess feasibility and preliminary efficacy. 24 participants will be randomized to a health and wellness control condition and 24 to the experimental treatment condition.

3 * Describe the relevant prior experience and gaps in current knowledge. Describe any relevant preliminary data:

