We're following up about your participation in a VA research study. It's time to schedule our final meeting so we can update you on our progress. Please use the following link to show when you are available for this meeting. If you have any trouble with the scheduling link or would like speak with a study team member you can email us at [contact] or contact us at XXX-XXX-XXXX.

We cannot guarantee email is secure so please do not reply back to this message with any personal information or personal health information.

Thank you and have a great day!

3. Email script 2 for EAP scheduling

Subject: research study follow up

Hello,

We're following up about your participation in a VA research study. Based on everyone's availability, we are hoping to schedule the meeting for DATE at TIME. The meeting will take place at LOCATION (phone/telehealth/in person). Please reply YES or NO to this email to confirm this works for you. If you had any trouble with the scheduling link or would like speak with a study team member you can email us at [contact] or contact us at XXX-XXX-XXXX. We cannot guarantee email is secure so please do not reply back to this message with any personal information or personal health information.

Thank you and have a great day!

Aim 3 quantitative data will be collected at baseline, post-RCT participation, and 3 month and 6 month follow-up and qualitative data will be collected at 3 month or 6 month follow-up. Feasibility will be assessed with study administration data on engagement and participation in the intervention and preliminary efficacy will be evaluated via coded Veteran/provider encounters and quantitative analysis of functioning from self-report surveys. Further needed intervention modifications will be identified from qualitative interviews.

Participants will have the option of completing the surveys in person, by phone, or by mail. If participants completing the surveys by mail have not returned the surveys within one week a study team member will follow-up by phone. Participants completing the surveys by phone or mail will be mailed their participation compensation upon receipt of the survey data.

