Appointment recording coding. Similar to the procedures described in 3b11 (Aim 1 data analysis), the PI will work with two research team staff members to code recorded appointments with the MPCC. We will all code the first 4 recordings to confirm coder competence and establish interrater reliability. After the first 4 recordings coders will code recordings individually until every seventh recording. Every seventh recording I and the research team members will again all code the same recording and check for agreement. Through this process 20% of the recorded appointments will be coded and compared by multiple coders.

Aim 3, hypothesis 3a. The brief, Veteran-targeted, PCI will be shown to be feasible as evidenced by adequate rates of recruitment, Veteran attendance at PCI sessions, and interventionist fidelity to the PCI. We will track: (1) actual recruitment compared to recruitment goals; (2) number of sessions each participant attends, enabling us to identify initial engagement, overall attendance rates, and drop-out; (3) number of reminder and outreach contacts required to keep participants engaged, indicating how much staff time is required to successfully facilitate involvement; (4) interventionist adherence to the PCI; and (5) qualitative feedback from a subsample of pilot RCT intervention arm participants as described in section 3d9. Recruitment feasibility will be assessed by a proportion equal to # of patients who sign consent / # of patients approached. To account for sampling variability we will also calculate a 95% confidence interval. Attendance will be collected at each PCI session and stored in our database. We will calculate the proportion of sessions attended for each participant. Feasibility will be demonstrated if at least 80% of PCI participants attend at least 2 out of 3 of PCI sessions. Interventionist fidelity will be measured by our interventionist adherence rating scale. A random selection of 25% of the PCI session recordings will be analyzed, stratified by month over the course of the pilot RCT, to examine potential changes in the way the PCI is delivered over time. After study completion we will calculate overall percentages for each item of the scale to assess overall fidelity. Interventionist fidelity will be demonstrated if at least 90% of interventionist behaviors in the analyzed PCI sessions have been rated acceptable or excellent.

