Aim 3, hypothesis 3b. We hypothesize that compared to control participants, participation in the brief, Veteran-focused, PCI will result in significantly greater increase in (1) Veteran PCC behaviors in mental health care encounters as measured by the MPCC and (2) functioning in domains of health, purpose, and community as measured by the VR-36 and WHODASS. Our overall approach will be to compare group means using a mixed model, accounting for common providers among participants with a random provider effect. If

an out of balance prognostic covariate is found in baseline comparisons this variable will also be included in the model, although the number of covariates that can be adjusted for will be limited by the sample size. We chose to use mixed models versus GEE (generalized estimating equations) to avoid bias due to unequal cluster sizes or sample size.

More specifically, for hypothesis 3b(1) to compare the treatment arms on PCC behaviors in mental health care encounters we will use the MPCC, assessed only at time point 2. The independent variable will be the treatment group indicator. For hypothesis 3b(2) to examine whether relative to control the treatment group has greater functioning (subscales of the VR-36 and WHODAS), we will compare group means at time points 3 and 4 using a linear mixed model ANCOVA. The comparison at time point 3 will be primary and at time point 4,

secondary. For this hypothesis, after adjustment for baseline, there will be 2 repeated measures (time points 3 and 4) which will be assumed to be correlated (i.e. thru correlated error terms). However, contrasts will be specified in order to compare the groups at time point 3, separately from time point 4.

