Qualitative semi-structured interviews. Following the 3rd time point some participants (n=12) who attended all three intervention sessions will complete a qualitative semi-structured interview and some participants (n=5) who completed one or two intervention sessions will complete a qualitative semi-structured interview. Participants will be asked about their experience with the PCI, their thoughts about its overall utility, and their experiences participating via telehealth if their participation was impacted by the COVID-19 pandemic. This will include review of the format and content of the sessions, handouts, and educational materials. Interviews will begin with broad open questions about initial reactions, explore those thoroughly, and subsequently ask specific follow up questions to elicit information about each facet of the intervention and telehealth. After each interview the interviewer will append a field note documenting pertinent observations. Interviews will be in-person or by phone and recorded for verbatim transcription to facilitate coding.

Aim 3 analysis of semi-structured interviews. We will use qualitative RAP to analyze the semi-structured interviews. RAP is ideal for PAR studies with action-oriented goals: it uses team-based coding and focuses data analysis in order to answers to specific research questions.

ID: VIEW4E02806052800
Name: v2_Sample Size and Data Analysis

Sharing of Results

1 * Describe whether results (study results or individual subject results, such as results of investigational diagnostic tests, genetic tests, or incidental findings) will be shared with subjects or others (e.g., the subject's primary care physicians) and if so, describe how it will be shared:

Overall study results will be shared through publications. Per mandatory data sharing, final datasets will be maintained locally until enterprise-level resources become available. Final data sets will be made available to the public upon request. Specifically, complete person-level data will be provided as either a Limited Dataset or as a de-identified, anonymized dataset depending on the needs of the requester.

ID: VIEW4E02808CBD800
Name: v2_Sharing of Results

Psychological/Behavioral/Educational Methods & Procedures

You indicated on the "Type of Research" page that your study involves a psychological/behavioral/educational method or procedure such as a survey, questionnaire, interview, or focus group.

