- If meeting face-to-face with a veteran for their individual session(s) is not possible then a trained study interventionist may (1) transport a study audio recorder to capture the audio of any individual session(s) completed via telehealth visit or (2) utilize the VA's protocol for Recording in CAG using Audacity Application and will export the recording to a restricted access VA sharedrive. If the interventionist uses an audio recorder they will utilize their locked HIPAA bag to transport the recorder, to ensure its protection.

- If meeting face-to-face with a veteran for their regularly scheduled mental health care is not possible and the veteran has provided consent to record one of their regularly scheduled mental health care appointments, then the study team will approach the veteran's mental health care provider to ask if they are willing to utilize the VA's protocol for Recording in CAG using Audacity Application. If they agree then the study team will make arrangements with the clinician to receive the recording via a sharedrive and immediately export the recording to a restricted access VA sharedrive.

Behavioral Intervention

You indicated that this study involves psychosocial or behavioral interventions.

1 * Describe the intervention (duration, number of sessions, focus, etc.):

Aim 3

Treatment condition. We anticipate that the person-centered intervention (PCI) will be comprised of three, one-hour sessions offered over three to six weeks, scheduled at the participants' preference. Sessions will be one-on-one with the interventionist. The PCI sessions will be offered in a private room in the same buildings that VA mental health services are located in, on the two respective VAMHCS campuses OR will be offered via VA Video Connect, the VA's telehealth program which uses encryption to ensure a secure and private session, OR phone.

Control condition. The control condition will be an educational health and wellness intervention for stress related disorders that will match the experimental condition for time and attention. The control condition will be three, one hour, individual sessions covering the symptom cycle, managing stress, and identifying social supports. The interventionist will be a non-blinded member of the research team such as the

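### The plan allows one-hour feedback interviews, held in the PCI arm only (up to 17 of 24 Veterans), to take place before the 6-month assessment, with no matching contact for controls

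*Combined protocol and SAP*

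**What the plan says.** All references are to the combined protocol and SAP.

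- **Allocation** (Justification, Objective, & Research Design, item 2): "24 participants will be randomized to a health and wellness control condition and 24 to the experimental treatment condition".
- **Control** (Behavioral Intervention, item 1): both arms get three one-hour individual sessions, and the control is meant to "match the experimental condition for time and attention".
- **Who is interviewed** (Sample Size and Data Analysis, item 2, on the Aim 3 qualitative interviews): "Following the 3rd time point some participants (n=12) who attended all three intervention sessions will complete a qualitative semi-structured interview". The same sentence adds 5 Veterans with only one or two sessions. The text on hypothesis 3a places the interviews in one arm, as "qualitative feedback from a subsample of pilot RCT intervention arm participants". No interview or equivalent contact is described for controls.
- **Content** (same qualitative section): questions cover the Veteran's experience of the PCI and its usefulness, and "This will include review of the format and content of the sessions, handouts, and educational materials". Interviews, item 3, gives the length as one hour.
- **Timing**: the qualitative section sets a start, after the third time point, but no end. Study Procedures, item 1, says "qualitative data will be collected at 3 month or 6 month follow-up".
- **What is measured at or up to TP4** (Sample Size and Data Analysis, item 2): for functioning, "we will compare group means at time points 3 and 4 using a linear mixed model ANCOVA", with time point 3 primary and time point 4 secondary. Symptom measures are also taken at TP4, and missed or cancelled appointments are counted from TP3 to TP4.

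**The concern.** The control was chosen so that a difference between arms would not simply reflect more time with study staff. A one-hour conversation that takes a Veteran back through PCI sessions and handouts, offered in one arm only, is contact that the control does not match. If it happens before TP4, a 6-month difference could mix the lasting effect of the three-session PCI with whatever the interview adds. It would also fall inside the TP3-TP4 window in which missed appointments are counted. The Supporting Literature section itself stresses that Veterans need time to reflect on goals and priorities, so a guided return to the material may not be neutral. What is at stake is a clean reading of the 6-month results.

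**Working it through.** **1. Timeline.** Study Procedures lists four assessments: baseline, post-participation, 3 months and 6 months. Read in order, these are TP1 to TP4. The sample-size paragraph labels TP3 as post-treatment, which should be reconciled; the reading here follows Study Procedures.

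| Interview slot | Allowed by | Position relative to TP4 |
|---|---|---|
| 3-month follow-up | Study Procedures; consistent with the qualitative section | Before, by about three months |
| 6-month follow-up | Study Procedures; consistent with the qualitative section | Same visit, order not stated |

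No text fixes the order of interview and TP4 questionnaires. The number interviewed before TP4 can therefore be anything from 0 to 17.

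**2. Share of the arm.**
- Planned interviews: 12 + 5 = 17.
- Of those randomised to PCI: 17/24 = 70.8%.
- Of the 19 expected with TP3 data: 17/19 = 89%.
- Expected at TP4, with 30% loss: 24 x 0.70 = 16.8. The interviewed share of analysed PCI Veterans could run from none to nearly all.

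**3. Contact time, if all 17 interviews came before TP4.**
- 12 full attenders: 3 h + 1 h = 4 h, against 3 h of control sessions.
- 5 partial attenders: 1-2 h + 1 h = 2-3 h, no more than the planned 3 h.
- Remaining 24 - 17 = 7: no interview.
- Mean added per randomised PCI Veteran: 17/24 = 0.71 h, or 0.71/3 = 24% of the planned 3 h.

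The minimum, with no interview before TP4, is 0 h.

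**4. The plan's own power figure, to fix the scale.** Inputs are 19 per arm, d = 0.65 and r = 0.7. A two-sided 5% test is assumed, because the plan does not state alpha.
- Residual SD = sqrt(1 - 0.7²) = 0.714.
- SE = 0.714 x sqrt(2/19) = 0.232.
- Power = Φ(0.65/0.232 - 1.96) = 0.801. The stated 0.80 is reproduced (0.779 with a noncentral t on 35 df).

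**5. Illustration at TP4.** The documents give no interview effect, so this is assumption only. Suppose 17/24 of analysed PCI Veterans were interviewed first and the interview shifted each one's TP4 score by b SD. With 17 analysed per arm, SE = 0.714 x sqrt(2/17) = 0.245.

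| Assumed b | Shift in TP4 contrast (17/24 x b) | Rejection of a true null (t test, 31 df) |
|---|---|---|
| 0 | 0 | 5.0% |
| 0.1 | 0.07 SD | 5.9% |
| 0.2 | 0.14 SD | 8.7% |
| 0.3 | 0.21 SD | 13.4% |

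If no interview comes before TP4, the shift is 0 and the rate is 5.0% whatever b is.

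**The case against.** A reader might infer that 17 Veterans will receive a fourth PCI session before TP4 and that the 6-month comparison has therefore lost its attention-matched control. The documents do not support that reading, for three reasons.

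- Interviewing before TP4 is permitted, not required; the 6-month slot is equally open.
- The contact is a feedback interview that opens with broad questions about reactions. The Aim 2 interview is described in nearly the same terms and is plainly there to collect feedback. Nothing describes re-teaching or goal-setting, and any therapeutic effect is conjecture.
- The match refers to the three one-hour sessions in each arm, and those remain equal. A rise from 3 to 4 hours can apply to at most the 12 full attenders.

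The extra $50 for interviewees (Payment/Reimbursement Detail, item 3) might also be thought to raise TP4 retention in the PCI arm. That is speculation: assessments carry the same $50 payment with no difference between arms stated.

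The exposed results are also not the main ones. The communication measure (MPCC) is taken at TP2, the primary functioning contrast is at TP3, the plan calls the symptom analyses exploratory, and the stated primary goal is feasibility, to which the interviews contribute.

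All of this stands and limits the severity. It does not close the gap: the 3-month slot is expressly allowed, only one arm is interviewed, and TP4 is a pre-specified comparison.

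**Conclusion.** The point holds as a minor gap in scheduling. The plan does not protect the attention match at TP4; it does not certainly break it. Between 0 and 17 of 24 PCI Veterans may have one extra hour of unmatched contact before TP4, a mean of at most 0.71 h per randomised PCI Veteran. The direction and size of any effect on outcomes are unknown, and the 0.1-0.3 SD range above is illustrative only. The results exposed are the secondary TP4 functioning contrast, the exploratory TP4 symptom analyses and the TP3-TP4 missed-appointment outcome. MPCC at TP2 and the primary TP3 contrast are not affected, provided interviews follow the TP3 assessment. The conclusion rests on reading TP3 and TP4 as the 3-month and 6-month follow-ups.

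**What to change.** In Study Procedures (item 1) and in the Aim 3 qualitative interview text, state that each interview takes place only after that Veteran's TP4 questionnaires are complete, or after the Veteran has been recorded as missing TP4. Remove the 3-month option. The documents define no TP4 window, so the rule for recording TP4 as missed should be written down too.

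For interviews already held, record the dates, report how many came before TP4, and say so when interpreting the TP4 results.

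The change needs wording and scheduling only, since the 6-month slot is already allowed. The cost is that recall of the sessions will be up to three months older. With 30% loss expected at TP4, the targets of 12 and 5 interviews may also not be fully met, and partial attenders are an informative group for feasibility. Allowing interviews with Veterans already recorded as missing TP4 limits that loss.

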5.1 If Yes, what procedures are in place to assure safety?

ID: VIEW4E0947A633C00
Name: v2_Interviews

Focus Groups

You indicated that this study involves focus groups or semi-structured group discussions.

1 * Are any of the questions likely to cause discomfort in participants or cause harm if their confidentiality were breached? (i.e., Illegal activities)

Yes No

2 * Upload a copy of the interview script or guide that will be used to guide the interviews:

Name	Created	Modified Date
 Focus Group Script.docx(0.01)	10/20/2016 4:13 PM	10/20/2016 4:13 PM

3 * How much time are the groups expected to require?
90 minutes

4 * How will the data be recorded?
Detailed notes will be taken by research staff.

5 * Do any questions elicit information related to the potential for harm to self or others?
 Yes No

5.1 If Yes, what procedures are in place to assure safety?

ID: VIEW4E094A8F91800
Name: v2_Focus Groups

Audio or Video Recording/Photographs

You indicated that this study involves audio or video recording/photographing.

1

* Indicate the type of recording (check all that apply):

- Video
- Audio
- Still Photo
- Other

1.1

If Other, specify:

2

* What is the purpose of the recording? (i.e., for therapeutic purposes, to establish treatment fidelity, or to establish reliability of assessments)

Aim 1 = We audio recorded the participant-provider encounters for the purpose of capturing Veteran and provider PCC behaviors in mental health care encounters.

Aim 2 (acceptability trial participants only) & Aim 3 = We will be audio recording the qualitative interviews in order to capture main themes and understand the perspective of Veterans. We are also audio recording the individual sessions in order to provide feedback and train/supervise study staff on the intervention. After the individual sessions are complete the veteran will decide if they would like to participate in an optional one-time audio recording of one of their regularly scheduled mental health appointments to see if the study had an impact on their behavior.

3

* Could the recording be likely to cause discomfort in participants or cause harm if their confidentiality were breached?

- Yes
- No

4

* How will individuals' identities be protected?

Audio recordings will not be labeled with any identifying information. They will be stored electronically, in a restricted access folder (accessible only to study staff) behind the VA firewall.

Audio recordings of encounters and interviews will be transcribed by an outside VA-approved transcription agency, so as to not have the actual audio recording be the only copy of this research data. Electronic files of audio recordings will be electronically uploaded to our VA-Approved Transcription agency's website (encrypted) in order for them to transcribe the encounters and interviews.

Audio recording of individual sessions will be protected in the same manner listed above. They are stored electronically in the same manner listed above.

- If meeting face-to-face with a veteran for their individual session(s) is not possible then a trained study interventionist may (1) transport a study audio recorder to capture the audio of any individual session(s) completed via telehealth visit or (2) utilize the VA's protocol for Recording in CAG using Audacity Application and will export the recording to a restricted access VA sharedrive. If the interventionist uses an audio recorder they will utilize their locked HIPAA bag to transport the recorder, to ensure its protection.

- If meeting face-to-face with a veteran for their regularly scheduled mental health care is not possible and the veteran has provided consent to record one of their regularly scheduled mental health care appointments, then the study team will approach the veteran's mental health care provider to ask if they are willing to utilize the VA's protocol for Recording in CAG using Audacity Application. If they agree then the study team will make arrangements with the clinician to receive the recording via a sharedrive and immediately export the recording to a restricted access VA sharedrive.

Behavioral Intervention

You indicated that this study involves psychosocial or behavioral interventions.

1 * Describe the intervention (duration, number of sessions, focus, etc.):

Aim 3

Treatment condition. We anticipate that the person-centered intervention (PCI) will be comprised of three, one-hour sessions offered over three to six weeks, scheduled at the participants' preference. Sessions will be one-on-one with the interventionist. The PCI sessions will be offered in a private room in the same buildings that VA mental health services are located in, on the two respective VAMHCS campuses OR will be offered via VA Video Connect, the VA's telehealth program which uses encryption to ensure a secure and private session, OR phone.

Control condition. The control condition will be an educational health and wellness intervention for stress related disorders that will match the experimental condition for time and attention. The control condition will be three, one hour, individual sessions covering the symptom cycle, managing stress, and identifying social supports. The interventionist will be a non-blinded member of the research team such as the

PI or coordinator. The control sessions will be offered in a private room in the same buildings that VA mental health services are located in, on the two respective VAMHCS campuses OR will be offered via VA Video Connect, the VA's telehealth program which uses encryption to ensure a secure and private session, OR phone.

ID: VIEW4E0BC12A9F800
Name: v2_Behavioral Interventions

Data Collection/Record Review

You indicated on the "Type of Research" page that your study involves data collection or record review (i.e., chart review, not self-report).

1 * What type of data will be collected/analyzed in this study? (Check all that apply)

Retrospective/Secondary Analysis (data has already been collected at the time of initial IRB submission)
 Prospective (data is not yet in existence and/or collected)

2 * Will this study involve adding data to a registry or database for future use?

Yes No

3 * Will the data be released to anyone not listed as an investigator on the protocol?

Yes No

3.1 If Yes, give name(s) & affiliation(s):

ID: VIEW4E0E25A8CA400
Name: v2_Data Collection / Record Review

Prospective Data

You indicated that the study involves the collection of prospective data.

1 * Where is the data being collected from? (Check all that apply)

- Medical records
- Medical images
- Commercial (for profit) entity
- Publicly available records
- Schools
- Other

1.1 If Other, please specify:

2 * What data fields will you have access to/collect for the study? For example, name, initials, date of birth, Social Security number, income, demographic information, family units, housing, etc.

The following information will be collected from VA medical records: 1) Veteran name 2) Veteran address 3) period of military service 4) mental health/substance use diagnoses 5) initial date of mental health and/or alcohol/drug abuse treatment service use 6) last date of mental health and/or alcohol/drug abuse treatment service use.

Near the end of study participation, Veteran service use data will be collected for the period of time the Veteran was enrolled in the study. This will include number of mental health, physical health, and Whole Health appointments and appointment dates.

You can also upload a copy of the data fields/variables to be collected for the study:

Name	Created	Modified Date
------	---------	---------------

There are no items to display

ID: VIEW4E0E25B643800
Name: v2_Prospective Data

Clinical Trial Registration

You indicated on the "Type of Research" page that your study is a clinical trial.

1 * Does the UM Clinical Trials Registry policy require registration of this trial?
 Yes No

2 * Has this trial been registered?
 Yes No

ID: VIEW4E093BF078C00
Name: v2_Clinical Trial Registration

Clinical Trial Registration Information

You indicated that this clinical trial has been registered.

1 * Was this trial registered at www.clinicaltrials.gov?
 Yes No

2 If no, was this trial registered on a site other than clinicaltrials.gov?
 Yes No

2.1 If Yes, specify the name of the other site:

2.2 Provide justification for registering this trial on this site:

3 * Registration Number
NCT02943408

ID: VIEW4E093BF1D0800
Name: v2_Clinical Trial Registration Information

Participant Selection

1 * How many local potential participants (or specimens/charts) do you anticipate will be screened for this study? **Screening includes determining potential participants' initial eligibility for and/or interest in a study.**
4000

2 * How many participants (or specimens, or charts) will be enrolled/used for this study? **A local prospective participant is considered enrolled in the study when a UM-approved Informed Consent Document (not including separate screening consent forms) is signed.**

Local - the number being enrolled at this site:

171

Worldwide - the number being enrolled total at all sites (including local enrollment):

171

3 * Gender:

Male
 Female

4 * Age(s):

0 to 27 days (newborn infants)
 28 days to 12 months (Infant)
 13 months to 23 months (Toddler)
 2 to 5 years (Preschool)
 6 to 11 years (Child)
 12 to 17 (Adolescents)
 18 to 88 years (Adult)
 89 years and older

5 * Race/Ethnicity:

All Races Included
 American Indian or Alaskan Native
 Asian/Other Asian
 Asian/Vietnamese
 Black or African American
 Hispanic or Latino
 Mixed Race or Ethnicity
 Native Hawaiian or Pacific Islander
 White or Caucasian

6

* Language(s):

English
 Chinese
 French
 Italian
 Japanese
 Korean
 Local Dialect

- Spanish
- Vietnamese
- Other

6.1 Specify Other:

7

